Liver injury	An SAE of 'toxic hepatitis' was reported in a participant in a Phase 2 Crohn's disease study who received guselkumab CI IV at Weeks 0, 4, and 8, and CI SC at Week 12. This event may represent drug-induced liver injury (DILI) possibly related to guselkumab (see Section 5.13.3 in the IB). Transaminase increases have been identified as an adverse reaction of guselkumab. In 2 Phase 3 psoriatic arthritis studies, increased ALT and/or AST was observed more frequently in patients treated with guselkumab CCI compared to patients treated with guselkumab CCI or placebo.	status that may indicate a possible malignancy. Participants who develop a malignancy during the study (with the exception of no more than 2 localized basal cell skin cancers that are treated with no evidence of recurrence or residual disease) will be discontinued from study intervention (Section 7.1). During the conduct of the study, liver function tests will be monitored at regular intervals in accordance with regulatory guidance (FDA 2009). In addition, the induction doses evaluated in this clinical program will not exceed CC Participants with marked liver enzyme elevations or symptoms or signs of liver dysfunction (eg, jaundice), should undergo a thorough investigation for possible causes of liver injury (Appendix 9, Section 10.9). A participant must have their study intervention discontinued if the participant has severe liver test abnormalities that are not transient and are not explained by other etiologies (Section 7.1).
Immunosuppression	It is unknown if guselkumab in combination with other immunosuppressives increases the risk of diseases associated with immunosuppression, such as infections or malignancy.	• In order to minimize the theoretical increased risk of infection or malignancy with the combination of guselkumab with immunosuppressive therapy, the baseline dose of oral corticosteroids on study entry is limited to ≤40 mg prednisone or its equivalent per day, or 9 mg/day of budesonide, or 5 mg/day beclomethasone, which must be tapered from Week 12 onwards. Furthermore, participants receiving AZA, 6-MP, or MTX, must have been taking them for ≥12 weeks and been on a stable dose for at

Potential Risks of Clinical Significance	Summary of Data/ Rationale for Risk	Mitigation Strategy

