- 8. Have screening laboratory test results within the following parameters, and if 1 or more of the laboratory parameters are out of range, a single retest of laboratory values is permitted during the approximately 5-week screening period:
 - a. Hemoglobin ≥8.0 g/dL

- b. White blood cells (WBCs) $\geq 3.0 \times 10^3 / \mu L$
- c. Neutrophils $\ge 1.5 \times 10^3/\mu L$
- d. Platelets $\geq 100 \times 10^3 / \mu L$
- e. Serum creatinine ≤1.5 mg/dL
- f. Alanine transaminase (ALT) (or aspartate transaminase [AST]) \leq 2 x upper limit of normal (ULN)
- g. Total bilirubin (TBili) ≤ 1.5 x ULN (Isolated total bilirubin > 1.5 x ULN is allowed for those participants with known Gilbert's syndrome. Gilbert's syndrome is suggested by direct bilirubin $\leq 30\%$ [Palmer 2020].)

Tuberculosis

9. A potential participant is considered eligible if the participant meets all of the following TB screening criteria:

Note: Interferon gamma release assay (IGRA) testing includes either QuantiFERON-TB® or T-SPOT®.TB.

- a. Have no history of active TB or show signs or symptoms suggestive of active TB upon medical history and/or physical examination at screening.
- b. Have no history of latent TB prior to screening. An exception is made for participants who have a history of latent TB AND who satisfy one of the following criteria:
 - 1) Currently receiving treatment for latent TB

OR

2) Will initiate treatment for latent TB prior to the first administration of study intervention

Note: For participants with a history of treated latent TB there must be documentation of appropriate treatment prior to the first administration of study intervention. It is the responsibility of the investigator to verify the adequacy of previous TB treatment and provide appropriate documentation. IGRA testing is not required at screening for participants with a history of treated latent TB or ongoing treatment for latent TB.

- c. Have had no recent close contact with a person with active TB. If there has been contact, such participants are referred to a physician specializing in TB to determine if treatment is warranted or not. This evaluation must be adequately documented and, if treatment is recommended, the participant must be receiving appropriate treatment prior to the first administration of study intervention.
- d. Have a negative IGRA test result within 2 months prior to the first administration of study intervention, or who:

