9.4.5. Safety Analyses

All safety analyses will be based on the Safety Analysis Set. For the safety analyses, participants will be analyzed according to the study intervention they actually received regardless of the study intervention they were randomized to.

Adverse Events

The verbatim terms used in the eCRF by investigators to identify AEs will be coded using the Medical Dictionary for Regulatory Activities. Any AE occurring at or after the initial administration of study intervention through the day of last dose plus 12 weeks is considered to be treatment-emergent. All reported treatment-emergent AEs will be included in the analysis. For each AE, the percentage of participants who experience at least 1 occurrence of the given event will be summarized by intervention group.

Summaries, listings, datasets, or participant narratives may be provided, as appropriate, for those participants who die, who discontinue intervention due to an AE, or who experience a severe or an SAE.

Clinical Laboratory Tests

Laboratory data will be summarized by type of laboratory test. Reference ranges and markedly abnormal results (specified in the SAP) will be used in the summary of laboratory data. Descriptive statistics for changes from baseline in clinical laboratory results will be summarized by treatment group.

Suicidal Ideation and Behavior

Suicidal ideation and behavior based on the C-SSRS and AEs will be summarized descriptively.

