5.6.3. Additional Safety Assessments

5.6.3.1. Clinical Laboratory Tests

Blood samples for serum chemistry and hematology will be collected. The following tests will be performed by the central laboratory.

Hematology assessments will include but are not limited to the following: hemoglobin, hematocrit, platelet count, total and differential WBC count.

Blood chemistry assessments will include but are not limited to the following: chemistry panel (total and direct bilirubin, ALT, AST, alkaline phosphatase, albumin, total protein, calcium, phosphate, sodium, potassium, chloride, blood urea nitrogen /urea, and creatinine).

The baseline value for a participant is the value closest to but prior to the first dose of study agent. In addition, change from baseline is defined to be the assessment at the post-baseline visit minus the assessment at baseline. There will be no imputation for missing laboratory values.

Clinical laboratory test values are to be graded based on modified National Cancer Institute Common Terminology Criteria for Adverse Events (NCI-CTCAE) version 5.0 (Appendix 3) except ALT, AST, total bilirubin (TBili), and alkaline phosphatase which will be graded using the predefined upper limit of normal (ULN) thresholds. The laboratory tests not included in the table Laboratory Toxicity Grading in Appendix 3 or the predefined ULN thresholds of liver tests will not be presented in the tables or listings.

The following summaries of clinical laboratory tests will be provided for participants in the Safety Analysis Set:

- Laboratory parameters and change from baseline in laboratory parameters (hematology and chemistry).
- Summary of maximum NCI-CTCAE toxicity grade for post-baseline laboratory values for the predefined hematology and chemistry lab parameters except ALT, AST, total bilirubin, and alkaline phosphatase.
- Shift tables for maximum NCI-CTCAE toxicity grade from baseline will be summarized for the predefined hematology and chemistry lab parameters except ALT, AST, total bilirubin, and alkaline phosphatase.
- Summary of maximum postbaseline measurement for ALT, AST, total bilirubin, and alkaline phosphatase relative to ULN threshold.
- Line graphs will also be provided for ALT, AST, total bilirubin, and alkaline phosphatase.

Listings of participants with the following will also be provided:

- Abnormal post-baseline laboratory values of NCI-CTCAE grade \geq 3 except liver tests

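### The SAP plans no baseline-to-worst shift table for liver tests, so its ULN-band summary cannot separate elevations present at entry from new ones

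*SAP*

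**What the plan says.** SAP 5.6.3.1 grades most laboratory parameters on a modified NCI-CTCAE scale. The exceptions are ALT, AST, total bilirubin and "alkaline phosphatase which will be graded using the predefined upper limit of normal (ULN) thresholds". Parameters on the NCI-CTCAE scale get a table of maximum post-baseline grade and a table of shift from baseline to maximum grade. The shift tables "will be summarized for the predefined hematology and chemistry lab parameters except ALT, AST, total bilirubin, and alkaline phosphatase".

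For the four liver tests the SAP plans:

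- a "Summary of maximum postbaseline measurement for ALT, AST, total bilirubin, and alkaline phosphatase relative to ULN threshold", using the bands in Appendix 3;
- line graphs;
- a listing triggered by post-baseline ALT or AST at or above 5 x ULN, bilirubin at or above 2 x ULN, or ALP at or above 2 x ULN;
- a listing triggered by post-baseline ALT or AST at or above 3 x ULN together with bilirubin at or above 2 x ULN or INR above 1.5 at the same visit.

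The same section also plans "Laboratory parameters and change from baseline in laboratory parameters (hematology and chemistry"), with no exception for liver tests, and its chemistry panel includes all four. Protocol 9.4.5 agrees: "Descriptive statistics for changes from baseline in clinical laboratory results will be summarized by treatment group".

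Protocol 2.3.1 names liver injury as a risk and states: "Transaminase increases have been identified as an adverse reaction of guselkumab". Protocol 5.1, criterion 8, limits ALT (or AST) at screening to 2 x ULN and bilirubin to 1.5 x ULN. It adds that "Isolated total bilirubin > 1.5 x ULN is allowed for those participants with known Gilbert's syndrome". It lists no ALP limit.

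**The concern.** A shift table shows how many participants in the worst-value category were already there before treatment. The plan provides this for parameters such as sodium and potassium, but not for the four tests that bear on the liver risk named in the protocol. For those tests the categorical display starts after baseline. A participant who enters with ALT at 1.8 x ULN, ALP at 2.5 x ULN, or (with known Gilbert's syndrome) bilirubin at 2.2 x ULN, and does not change, appears in an elevated post-baseline band. The ALP and bilirubin cases also meet a listing trigger.

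At stake is how readable the hepatic safety tables are. Pre-existing elevations add the same expected proportion to every randomized column and pull the contrast toward no difference. After rescue, a placebo participant's persisting elevation is tabulated under guselkumab.

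**Working it through.** The documents state no figure on this point, so there is none to reproduce. The check compares entry limits with bands, looks at the other planned displays and the safety columns, and then illustrates the possible size.

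**1. Which bands can an unchanged entry value reach?** Limits are from Protocol 5.1, criterion 8; bands are from SAP Appendix 3; listing triggers are from SAP 5.6.3.1. All values are multiples of ULN.

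| Test | Entry limit | Bands | Reachable without any change |
|---|---|---|---|
| ALT, AST | 2 | >1 to <3; 3 to <5; 5 to <8; 8 or more | >1 to <3 only; no listing |
| Total bilirubin | 1.5, or higher if isolated with known Gilbert's syndrome | >1 to <2; 2 or more | >1 to <2; the upper band and its listing only with Gilbert's syndrome |
| ALP | none listed | >1 to <2; 2 to <4; 4 or more | any band; the listing at 2 or more |

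The protection of the higher ALT/AST bands is large but not complete. The limit is applied to screening results, and the wording ALT (or AST) leaves some doubt about AST.

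**2. Do the other displays fill the gap?** Change from baseline is summarized by parameter. It does not show which participants in a given ULN band were in that band at baseline. The line graphs are not specified to do so either. The SAP gives the listing triggers but not the columns, so whether baseline values would be shown is left open.

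**3. Which safety columns are affected, and how?** Through Week 12 the columns in SAP 5.6 are the randomized arms and the combined guselkumab group. In later summaries the placebo column still contains every placebo participant and drops only data after rescue. The two guselkumab arms and their combination are unchanged. Entry elevations therefore stay balanced in expectation across these columns. The placebo-to-guselkumab and all-guselkumab columns are not randomized groups, and both take in post-rescue values from placebo participants.

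**4. How large could the dilution be?** Let b be the share above ULN at entry and still above it at one or more post-baseline visits, which is enough because the table takes the maximum. Let e be the new-onset rate among the rest. The post-baseline-only table then shows

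observed rate = b + (1 - b) x e,

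and the observed risk difference is (1 - b) times the true one. The values of b and e are assumptions. For b = 5% with new onset of 5% on placebo and 10% on guselkumab:

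- placebo: 0.05 + 0.95 x 0.05 = 9.75%
- guselkumab: 0.05 + 0.95 x 0.10 = 14.5%
- risk ratio: 14.5 / 9.75 = 1.49
- risk difference: 4.75 points

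| b | 5% vs 10% new onset: ratio; difference | 2% vs 6% new onset: ratio; difference |
|---|---|---|
| 0% (what a shift table would show) | 2.00; 5.0 points | 3.00; 4.0 points |
| 5% | 1.49; 4.75 points | 1.55; 3.8 points |
| 10% | 1.31; 4.5 points | 1.31; 3.6 points |
| 20% | 1.17; 4.0 points | 1.15; 3.2 points |

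With the planned group sizes in Protocol 9.2, b of 5% to 20% means 106 x 0.05 = 5.3 to 106 x 0.20 = 21.2 placebo participants and 212 x 0.05 = 10.6 to 212 x 0.20 = 42.4 guselkumab participants above ULN post-baseline without a new elevation. The percentage is the same in both groups.

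**The case against.** The strongest defence is that the exception follows from the grading scheme. The planned shift tables use NCI-CTCAE grades, and liver tests are not graded that way. That explains why they are left out of those tables. It does not explain why the maximum-grade table has a ULN counterpart and the shift table has none.

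A second defence is that the serious end of the risk is well covered. A transaminase value within the entry limit cannot fill the bands at or above 3 x ULN or the listing at 5 x ULN. A stable participant with Gilbert's syndrome does not enter the combined listing without a transaminase rise. Drug-related hepatic disorders are adverse events of interest in SAP 5.6.2, and possible Hy's law cases are reported in an expedited manner under Protocol 8.3.1. All of this stands. It confines the point to the lowest ALT/AST band, bilirubin and ALP.

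Third, these are descriptive tables, and SAP 5.6 plans no formal safety comparisons. That is also right. No test or endpoint is affected, only what a reader can learn from the tables.

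A reader might infer three stronger things that the documents do not support:

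- **Liver tests are reported with no reference to baseline.** Change from baseline is planned for all chemistry parameters.
- **Randomization stops balancing entry elevations after Week 12.** That is true only of the placebo-to-guselkumab and all-guselkumab columns.
- **The summary would create a false excess on guselkumab.** In the randomized columns entry elevations are expected equally in each arm, so the expected effect is dilution.

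**Conclusion.** The gap is real but limited. The four liver tests are the only graded parameters without a baseline-to-worst categorical table, and the planned ULN-band summary cannot tell a new elevation from one present at entry. The affected cells are ALT/AST above 1 and below 3 x ULN; bilirubin above 1 and below 2 x ULN, with the higher band and its listing only in known Gilbert's syndrome; and every ALP band with the ALP listing.

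The size is unknown because the documents give no baseline prevalence of liver-test elevation. The illustrated attenuation, from 2.00 to between 1.49 and 1.17, rests on assumed entry shares of 5% to 20% and assumed new-onset rates of 5% and 10%. Diluting a safety contrast is the unhelpful direction, and the remedy is cheap, so the change is worth making. It would not alter any efficacy result or any hypothesis test.

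**What to change.** Keep the exception to the NCI-CTCAE shift tables. In SAP 5.6.3.1, add for each of ALT, AST, total bilirubin and ALP a shift table of baseline ULN band by maximum post-baseline ULN band, by treatment column. Use the Appendix 3 bands plus a category for values at or below 1 x ULN. For the placebo-to-guselkumab column, state which value serves as baseline, since SAP 5.6.3.1 defines only the one before the first dose of study agent. Specify that both liver listings show the participant's baseline multiple of ULN.

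The cost is four extra descriptive tables and one added column in each of two listings. The bands and the baseline value are already defined, and no new data are needed.

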8.2.4. Clinical Safety Laboratory Assessments

Blood samples for serum chemistry and hematology will be collected as noted in the SoA (Section 1.3). The investigator must review the laboratory results, document this review, and record any clinically relevant changes occurring during the study in the AE section of the eCRF. The laboratory reports must be filed with the source documents.

The following tests will be performed by the central laboratory unless otherwise specified or approved by the medical monitor.

- **Hematology assessments** will include but are not limited to the following: hemoglobin, hematocrit, platelet count, total and differential WBC count.
- **Blood chemistry assessments** will include but are not limited to the following: chemistry panel (total and direct bilirubin, ALT, AST, alkaline phosphatase (ALP), albumin, total protein, calcium, phosphate, sodium, potassium, chloride, blood urea nitrogen /urea, and creatinine).
 - A medical monitor or delegate and the clinical site will be notified if prespecified abnormal laboratory values defined in the laboratory manual are identified in any participant during the conduct of the study.
- **Serology**: HIV antibody, HBV antibodies and surface antigen, and HCV antibody. For participants who are eligible with hepatitis B surface antigen (HBsAg) negative, hepatitis B core antibody (anti-HBc) and/or hepatitis B surface antibody (anti-HBs) positive, and HBV DNA test is negative, HBV DNA quantitation should be monitored according to local guidelines. Additional details are provided in Appendix 4 (Section 10.4).
- Abnormal liver function tests: If laboratory testing for a participant who is enrolled in the study and receiving study intervention reveals an increase of serum aminotransferases (ALT or AST) to ≥3 x ULN and an increase of bilirubin to ≥2 x ULN, study intervention should be suspended immediately. In addition, laboratory tests for ALT, AST, ALP, and TBili should be confirmed by a retest within 24 hours if possible, but no later than 72 hours following notification of test results. Additional clinical and laboratory studies may be performed to evaluate the underlying etiology of abnormal findings. See Appendix 9 (Section 10.9) for additional information on monitoring and assessment of abnormal liver function tests.

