8.3. Adverse Events, Serious Adverse Events, and Other Safety Reporting

Timely, accurate, and complete reporting and analysis of safety information (including AEs and SAEs) and PQCs, from clinical studies are crucial for the protection of participants, investigators, and the sponsor, and are mandated by regulatory agencies worldwide. The sponsor has established Standard Operating Procedures in conformity with regulatory requirements worldwide to ensure appropriate reporting of safety information; all clinical studies conducted by the sponsor or its affiliates will be conducted in accordance with those procedures.

Adverse events will be reported by the participant (or, when appropriate, by a caregiver, surrogate, or the participant's legally acceptable representative) for the duration of the study.

For study intervention that meets the definition of a combination product, malfunctions or deficiencies of a device constituent will be reported as PQC.

Further details on AEs, SAEs, and PQC can be found in Appendix 6 (Section 10.6).

8.3.1. Time Period and Frequency for Collecting Adverse Event and Serious Adverse Event Information

All Adverse Events

All AEs and special reporting situations, whether serious or non-serious, will be reported from the time a signed and dated ICF is obtained until completion of the participant's last study-related procedure, which may include contact for follow-up of safety.

Serious Adverse Events

All SAEs occurring during the study must be reported to the appropriate sponsor contact person by study site personnel within 24 hours of their knowledge of the event.

Serious adverse events, including those spontaneously reported to the investigator within 12 weeks after the last dose of study intervention, must be reported. The sponsor will evaluate any safety information that is spontaneously reported by an investigator beyond the time frame specified in the protocol.

A **possible Hy's law Case** is defined by the occurrence of ALT/AST \geq 3 x ULN together with TBili \geq 2 x ULN or international normalized ratio (INR) >1.5 (if measured). Any possible Hy's law case is considered an important medical event and should be reported to the sponsor in an expedited manner, even before all other possible causes of liver injury have been excluded.

A confirmed Hy's law case must be reported as an SAE.

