- 5. INR, and total protein and albumin (compute globulin fraction) should also be documented (to further scrutinize potential severity of the liver damage). If INR is abnormal, prothrombin time, partial thromboplastin time should be obtained and these values should be followed until normal, along with documentation of whether parenteral vitamin K was given along with the effect of such treatment on INR.
- 6. If initial LTs and ultrasound do not suggest Gilbert's syndrome, biliary tract disease or obstruction, viral hepatitis serology should be obtained including anti-hepatitis A virus immunoglobin (Ig)M, anti-hepatitis A virus total, HBsAg, anti-HBs, anti-HBc total, anti-HBc IgM, anti-HCV, anti-hepatitis E virus IgM (even if has not traveled to an endemic area for hepatitis E), Epstein-Barr virus, and cytomegalovirus screen.
 - If participant is immunosuppressed, test for HCV RNA and hepatitis E virus RNA by polymerase chain reaction.
 - If HBsAg or anti-HBc IgM or anti-HBc IgG positive, also get HBV DNA to detect active Hepatitis B, especially in patients who are immunosuppressed.
 - If all other hepatitis B serologic tests are negative and anti-HBc total is the only positive test, HBV DNA should be obtained to detect reactivation of hepatitis B.

Steps 7-12 are optional; In consultation with the Medical Monitor, additional clinical and laboratory studies may be performed to evaluate the underlying etiology of abnormal findings.

- 7. Based on potential baseline confounders of the disease target population consider (optionally): gamma-glutamyl transferase (to confirm the liver origin of elevated ALP levels), serum creatine phosphokinase (to confirm the liver origin of elevated AST levels], lactate dehydrogenase (to help exclude hemolysis), glutamate dehydrogenase (if muscle injury is suspected or if muscle disease is target population).
- 8. Assuming that the history, physical, and initial imaging and laboratory has not revealed a cause of elevated LTs, screen for other causes of liver disease including: antinuclear antibody, anti-liver kidney microsomal antibody type 1, anti-liver-kidney microsomal antibodies, anti-smooth muscle antibodies (to screen for additional immune-related etiologies), erythrocyte sedimentation rate, and CRP (to screen for potential systemic inflammatory causes).

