5.1.1. Visit Windows

Unless otherwise specified, nominal scheduled visits (described in SoA of the protocol) will be used for over time summaries and listings with no visit windows applied. However, the Unscheduled Visit (USV), Study Intervention Discontinuation (SID) and Final Efficacy and Safety (FES) visits will be slotted to scheduled visits according to the following mapping rules except for SES-CD endpoint:

- 1. Assign a visit number to USV, SID or FES visit based on the Study Day as illustrated in Table 2
- 2. If USV, SID or FES visit falls in the window of a scheduled visit and there are not already data for the scheduled visit, assign the scheduled visit number to the USV, SID or FES visit. If there are already data for a same scheduled visit, those data will be used in lieu of the USV, SID or FES visit data.

Week 4	Day 2-42
Week 8	Day 43-70
Week 12	Day 71-98
Week 16	Day 99-126
Week 20	Day 127-154
Week 24	Day 155-182
Week 28	Day 183-210
Week 32	Day 211-238
Week 36	Day 239-266
Week 40	Day 267-294
Week 44	Day 295-322
Week 48	Day 323-350
Week 52	Day 351-378
etc.	
Week 96	Day 659-686

Table 2: SID/FES/Unscheduled Visit Slotting

More frequent measurements are taken for other endpoints compared to endoscopic assessments taken only at Weeks 0, 12, 48, and 96.

For SES-CD endpoint using a wider window: +/- 4 weeks

Week 12: Days 57 to 113

Week 48: Days 309 to 365

Week 96: Days 645 to 701

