- Post-baseline elevated liver tests of ALT or AST \ge 5x ULN, or total bilirubin \ge 2x ULN, or alkaline phosphatase \ge 2x ULN
- Post-baseline elevated liver test with combined ALT or AST ≥ 3x ULN and (total bilirubin ≥ 2x ULN or INR > 1.5) at the same visit.

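### The SAP's combined ALT/AST and bilirubin/INR listing requires both abnormalities at one visit, so a potential Hy's law case split across two blood draws can go unlisted

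*SAP*

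**What the plan says.** - **SAP 5.6.3.1, combined listing.** It takes participants with "combined ALT or AST ≥ 3x ULN and (total bilirubin ≥ 2x ULN or INR > 1.5) at the same visit".
- **SAP 5.6.3.1, single-test listing.** It opens "Post-baseline elevated liver tests of ALT or AST" and takes ALT/AST at 5x ULN or more, total bilirubin at 2x ULN or more, or alkaline phosphatase at 2x ULN or more. Each counts alone, with no visit condition.
- **SAP 5.6.3.1, scope.** Tests outside the Appendix 3 grading table and the liver ULN thresholds are kept out of tables and listings. INR is in neither.
- **SAP 5.1.1.** Unless otherwise specified, over-time summaries and listings use nominal visits. Unscheduled, SID and FES results are slotted into day windows. Where the scheduled visit already has data, "those data will be used in lieu of the USV, SID or FES visit data".
- **Protocol 8.3.1.** A possible Hy's law case is ALT/AST at 3x ULN or more, with total bilirubin at 2x ULN or more or "international normalized ratio (INR) >1.5 (if measured"). No visit or interval is given. Appendix 9 restates the criterion, also without one.
- **Protocol Appendix 9.** Testing is repeated at 48 to 72 hours after an initial ALT or AST elevation. The liver panel includes ALT, AST and bilirubin but not INR. INR enters at work-up step 5: "INR, and total protein and albumin (compute globulin fraction) should also be documented". It is not named in the 8.2.4 chemistry panel and has no row in the Schedule of Activities.
- **Protocol 8.2.4.** A separate rule applies when testing "reveals an increase of serum aminotransferases (ALT or AST) to ≥3 x ULN and an increase of bilirubin to ≥2 x ULN". Then "laboratory tests for ALT, AST, ALP, and TBili should be confirmed by a retest within 24 hours if possible, but no later than 72 hours".

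**The concern.** Liver injury is a named risk in Protocol 2.3.1. That section describes a serious event of toxic hepatitis in a Phase 2 Crohn's disease study, possibly drug-induced, and identifies transaminase increases as an adverse reaction. No data monitoring committee is planned.

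Scheduled chemistry is every 4 weeks to Week 24, every 8 weeks to Week 48 and every 16 weeks after that. Between those draws, the course of a liver abnormality is visible only in unscheduled samples. A listing restricted to simultaneous abnormalities could therefore omit a participant who meets the protocol's criterion across two draws a few days apart. In a listing where individual cases matter, that is worth preventing.

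**Working it through.** The plan gives no figure to reproduce. The check compares the triggers, applies the listing rules to possible patterns, and tests the slotting rule.

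**1. Which repeat can separate the two parts?**
- Protocol 8.2.4: starts when ALT/AST and bilirubin are both already raised. If both come from one draw, the case is complete and listed before the retest.
- Protocol Appendix 9: starts from ALT or AST alone. Bilirubin can first cross at this repeat, and INR is first measured in the work-up that follows.

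Only the Appendix 9 route can put the two parts on different draws.

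**2. Which patterns reach a listing?** The laboratory values are illustrative assumptions. ALT and bilirubin are multiples of ULN, and alkaline phosphatase is taken as below 2x ULN throughout.

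Rules applied:
- Combined: ALT ≥3 and (bilirubin ≥2 or INR >1.5) on one draw.
- Single-test: ALT ≥5 or bilirubin ≥2.

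| Pattern | Index ALT, bilirubin | Repeat ALT, bilirubin, INR | Repeat kept as own visit: combined / single | Repeat displaced under 5.1.1: combined / single |
|---|---|---|---|---|
| A | 4, 2.5 | 4, 2.5, 1.2 | yes / yes | yes / yes |
| B | 4, 1.2 | 3.8, 2.3, 1.2 | yes / yes | no / no |
| C | 4, 1.2 | 2.6, 2.3, 1.2 | no / yes | no / no |
| D | 4, 1.2 | 3.5, 1.5, 1.7 | yes / no | no / no |
| E | 4, 1.2 | 2.8, 1.5, 1.7 | no / no | no / no |

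A rule that pairs the two parts across draws captures all five.

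A third reading applies 5.1.1 test by test. INR has no scheduled value, so it would be assigned to the index visit and paired with the index ALT of 4. D and E would then be listed. B and C would not, because the scheduled bilirubin of 1.2 displaces the repeat. Whether a case appears therefore depends on a programming choice that the SAP does not state.

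**3. Would a repeat fall in the index visit's slot?** Take the nominal day as 7 × week + 1 (first dose on the randomization day). Add the visit window of 4 days through Week 12 or 7 days after, then 3 days for a 72-hour repeat.
- Week 12: 85 + 4 + 3 = 92. The slot ends on Day 98, leaving 6 days.
- Week 32: 225 + 7 + 3 = 235. The slot ends on Day 238, leaving 3 days.

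The same holds at all ten visits checked (Weeks 4, 8, 12, 16, 20, 24, 32, 40, 48 and 96), with 6 days to spare through Week 12 and 3 after. If 5.1.1 governs these listings, the scheduled result displaces the repeat.

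**4. INR.** Read literally, the scope sentence in SAP 5.6.3.1 keeps INR out of listings, while the combined listing depends on it.

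**The case against.** The case for leaving the text alone has real substance.

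- **Concurrent reading.** The protocol joins the two abnormalities without giving an interval, and a reader may take that to mean concurrent. The SAP rule is then a plausible implementation. This stands as a reading, but Appendix 9 measures INR after the ALT/AST trigger, so strict concurrence fits that part poorly.
- **Repeats carry the full panel.** ALT, AST and bilirubin are drawn together, so a repeat with both raised satisfies the rule if kept as its own visit (pattern B). This stands. The omission needs ALT/AST to have fallen below 3x ULN, or the repeat to be displaced.
- **Slotting may not apply.** SAP 5.1.1 concerns over-time outputs and allows exceptions, whereas the liver outputs are described as post-baseline or maximum values. This also stands: loss through 5.1.1 is a possible reading, not an established one.
- **Other displays exist.** There is the single-test listing, the summary and graphs of maximum liver values, hepatic adverse event reporting (SAP 5.6.2), and expedited SAE reporting of potential Hy's law cases (Protocol Appendix 9). These mitigate, but none pairs the two laboratory results.

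A reader might infer that the 8.2.4 retest, which "should be confirmed by a retest within 24 hours if possible, but no later than 72 hours following notification of test results", completes cases that the listing then misses. The documents do not support that, because this retest starts from a case that already has both parts. A reader might also infer that the combined listing is the only route by which a potential case reaches the study report. The displays above show otherwise.

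**Conclusion.** The point holds, at minor severity. The SAP adds a same-visit condition that the protocol definition does not state, and leaves it undefined for unscheduled liver samples.

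- With the repeat kept as its own visit, a case whose bilirubin crosses only after ALT/AST has dropped below 3x ULN is missing from the combined listing but appears on the single-test listing.
- A case with index ALT/AST of 3 to under 5x ULN that qualifies only through a later INR, with ALT/AST by then below 3x, is on neither listing. The exception is test-by-test slotting of the INR.
- If whole repeat visits are displaced under 5.1.1, even a repeat with both parts raised can disappear from both.

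The number of affected participants cannot be derived, since the documents give no expected count of potential Hy's law cases. It would be too strong to say that the study's hepatic conclusion would change. The patterns rest on assumed laboratory values and show what the rules do, not how often it would happen.

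**What to change.** Amend SAP 5.6.3.1 as follows:

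1. Replace the same-visit condition with a prespecified interval: ALT or AST at 3x ULN or more, with total bilirubin at 2x ULN or more or INR above 1.5 on the same day or within that interval afterwards. The length is for the sponsor to choose. Thirty days is one example and is an assumption, not a figure from the documents.
2. Use all post-baseline results, including unscheduled, SID, FES and any local-laboratory values.
3. State that 5.1.1 slotting does not apply to the liver listings or to maximum post-baseline liver values.
4. Exempt INR from the sentence that removes tests not covered by Appendix 3 or the liver thresholds.

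The cost is a few sentences and a small programming change. Some non-cases will be listed and need medical review, for example participants with Gilbert's syndrome, whom inclusion criterion 8 admits despite raised bilirubin. No change to patient monitoring is involved.
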